Intervention /Comparator	
Intervention arm: intermediate-dose anticoagulation
 
 • If stable eGFR ≥ 30 mL/min: enoxaparin 1mg/kg SC daily or unfractionated heparin infusion at 10 units/kg/hour with goal anti-Xa 0.1-0.3 U/mL.¹ • If eGFR <30 mL/min or acute kidney injury (as defined below) or CRRT: Unfractionated heparin infusion at 10 units/kg/hour (minimum 500 units/hour if CRRT) with goal anti-Xa 0.1-0.3 U/mL.² 
Control arm: prophylaxis
 
Prophylactic dose anticoagulation (per CUIMC Guidelines):
 
 • If eGFR ≥ 30 mL/min (stable kidney function): 
 ◦ BMI < 40 kg/m2: Enoxaparin 40 mg SC daily ◦ BMI 40 – 50 kg/m2: Enoxaparin 40 mg SC q12h ◦ BMI > 50 kg/m2: Enoxaparin 60 mg SC q12h • If eGFR < 30 mL/min or acute kidney injury: 
 ◦ 50-120 kg: Unfractionated heparin 5000 units SC q8h ◦ > 120 kg: Unfractionated heparin 7500 units SC q8h 
If CRRT: Unfractionated heparin infusion pre-filter at 500 units/hour

Primary Endpoint	
Primary outcome: Composite of being alive and without clinically-relevant venous or arterial thrombotic events at discharge from ICU (without transfer to another palliative care unit/hospice) or at (if ICU duration lasted 30 days or longer).
 
Clinically relevant venous or arterial thrombotic events will all be adjudicated and are defined as any of the following:
 
 Confirmed or treated deep venous thrombosis or pulmonary embolism Type I myocardial infarction (MI) as confirmed by a combination of biomarkers, electrocardiogram and angiogram New ischemic stroke Acute limb ischemia Actionable line thrombosis requiring escalation of anticoagulation or removal or replacement of the line CVVH Filter thrombosis requiring escalation of anticoagulation Other thrombotic events requiring anticoagulation (e.g., intracardiac thrombosis)

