Study intervention	
 Each cluster will be randomized to one of the two antithrombotic regimens: prophylactic-dose or intermediate dose as described above. The choice of agents will be dependent upon the renal function (at the time of enrollment and every subsequent day). At the onset of study enrollment, clusters including patients admitted within the past 5 days will be randomized. Patients who meet eligibility by screening team will be enrolled. Patient is considered enrolled after a co-investigator has confirmed all inclusion/exclusion criteria have been met. Assessment of appropriateness of anticoagulation dose will occur daily based on the renal function, progressive thrombocytopenia or anemia, or development of another indication for anticoagulation such as new-onset atrial fibrillation, Patients' treatment course will be followed from randomization to hospital discharge or 30 days, whichever happens earlier. Patients will continue with randomization therapy until discharged from the ICU, except in the setting of an adverse event attributed to anticoagulation, developing an event requiring therapeutic anticoagulation, or change in code status to comfort measures. Patients transferred between participating ICUs will remain in the treatment arm assigned at initial randomization. Recommendation will be to continue study treatment if patient transferred to ICUs not participating in the present trial. If the study treatment is changed by the primary treating team in the second ICU, then patient will be evaluated by intention to treat principle. 
Intervention arm: intermediate-dose anticoagulation
 
 If stable eGFR ≥ 30 mL/min: enoxaparin 1mg/kg SC daily¹ If eGFR <30 mL/min or acute kidney injury (as defined below) or CRRT: Unfractionated heparin infusion at 10 units/kg/hour (minimum 500 units/hour if CRRT) with goal anti-Xa 0.1-0.3 U/mL² 
Control arm: Prophylactic dose anticoagulation (per CUIMC Guidelines):
 
 If eGFR ≥ 30 mL/min (stable kidney function): 
 BMI < 40 kg/m²: Enoxaparin 40 mg SC daily BMI 40 – 50 kg/m²: Enoxaparin 40 mg SC q12h BMI > 50 kg/m²: Enoxaparin 60 mg SC q12h If eGFR < 30 mL/min or acute kidney injury: • If eGFR < 30 mL/min or acute kidney injury:

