	
 ○ 50-120 kg: Unfractionated heparin 5000 units SC q8h ○ > 120 kg: Unfractionated heparin 7500 units SC q8h • If CRRT: Unfractionated heparin infusion pre-filter at 500 units/hour
Study assessment and activities	
All anticoagulation medications are standard of care according to discussions between clinician leadership in multiple disciplines and review of treatment protocols from institutions in the region and internationally. Anticoagulants will be ordered through the hospital pharmacy.
 
Patient receiving any anticoagulation are at risk for development of hemorrhage, thrombocytopenia, and in rare cases (overall rate of 0.2%) heparin induced thrombocytopenia (7). Patients who have a bleeding event may have cessation of the administered drug per clinical standard of care, and in some cases may require transfusion of blood products, and additional testing and therapy to identify and treat the source of bleeding. Patients who develop a thrombotic event may have intensification of anticoagulation per clinical standard of care.
 
We will collect all clinical, laboratory and imaging data generated per standard of care throughout the patient's hospitalization. Primary and Secondary endpoints will be assessed at ICU discharge, hospital discharge and 30 days if the patient is still hospitalized.

III. Endpoint Definition

a) Endpoint Reporting Requirements

Safety surveillance and reporting starts as soon as the patient is enrolled in the clinical investigation and will continue until the subject is deceased, the subject concludes participation in the clinical investigation or the subject withdraws from the clinical investigation.
Endpoint data will be collected throughout the time period defined above and will be entered on a CRF.

For the purposes of this investigation the following are reportable endpoints:

Death	
Deep venous thrombosis	Diagnosed on duplex ultrasonography including upper (internal jugular, subclavian, axillary/brachial) and lower extremity (iliac, femoral/popliteal, gastrocnemius, peroneal, posterior tibial) thrombosis
Pulmonary embolism	Diagnosed on CT angiography, V/Q scan, or invasive pulmonary angiography

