Type I myocardial infarction	Detection of a rise and/or fall of cTn values with at least one value above the 99th percentile URL and at least one of the following: symptoms of ischemia, new or presumed new significant ST-segment-T wave (ST-T) changes or new left bundle branch block (LBBB); development of

	pathological Q waves on the ECG; imaging evidence of new loss of viable myocardium or new regional wall motion abnormality; identification of an intracoronary thrombus by angiography or autopsy
Ischemic stroke	Neurological dysfunction caused by focal cerebral, spinal, or retinal infarction based on pathological, imaging, or other objective evidence of cerebral, spinal cord, or retinal focal ischemic injury in a defined vascular distribution; or 2. clinical evidence of cerebral, spinal cord, or retinal focal ischemic injury based on symptoms persisting ≥ 24 hours or until death, and other etiologies excluded. Exclude hemorrhagic infarction.
Acute limb ischemia	Sudden decrease in limb perfusion that threatens limb viability with confirmed arterial obstruction based on duplex ultrasonography or invasive peripheral angiography
Actionable line thrombosis	Arterial or central venous catheter thrombosis that results in removal or replacement of catheter or initiation of therapeutic anticoagulation. Excludes use of indwelling tPA.
CVVH filter thrombosis	Filter thrombosis requiring exchange in order to resume continuous veno-venous hemofiltration (CVVH) or resulting in cessation of CVVH
Other thrombotic events requiring anticoagulation	For example atrial fibrillation, left ventricular thrombus, right ventricular thrombus, etc.
Acute kidney injury	KDIGO criteria: 1. Increase in sCr ≥ 0.3 mg/dL (≥ 26.5 $\mu\text{mol}/\text{L}$) within 48 hours; or 2. Increase in sCr ≥ 1.5 times baseline, which is known or presumed to have occurred within the prior 7 days; or 3. Urine volume < 0.5 mL/kg/h for 6 hours.
Serious bleeding	
 BARC 3 or 5 bleeding (3: decrease in the hemoglobin of > 3 g per deciliter, any transfusion, cardiac tamponade, or intracranial or ocular involvement; 5: fatal)

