	
 • ISTH major bleeding: 1: Fatal bleeding, and/or 2. Symptomatic bleeding in a critical area or organ, such as intracranial, intraspinal, intraocular, retroperitoneal, intraarticular or pericardial, or intramuscular with compartment syndrome, and/or 3. Bleeding causing a fall in hemoglobin level of 2 g/dL (1.24 mmol/L) or more, or leading to transfusion of two or more units of whole blood or red cells. • TIMI major bleeding: Any intracranial bleeding (excluding microhemorrhages ≤ 10 mm evident only on gradient-echo MRI), or Clinically overt signs of hemorrhage associated with a drop in hemoglobin of ≥ 5 g/dL, or Fatal bleeding (bleeding that directly results in death within 7 d
--	--

IV. Event Adjudication

A clinical events committee will be formed for adjudication of clinical endpoints. Suspected components of the primary endpoint as well as the secondary endpoints, including the bleeding endpoint as documented in case report forms will be adjudicated based on pre-defined clinical definitions of venous thromboembolism, myocardial infarction, ischemic stroke, acute limb ischemia, clinically-actionable line thrombosis, and major bleeding. All suspected events will be independently reviewed by two physicians blinded to randomized group assignment. If there is disagreement on whether an endpoint event has occurred, the case will be reviewed by the clinical events committee for adjudication.

V. Safety Monitoring Plan

All events outlined above will be reported to the Clinical Events Committee (CEC) and Data and Safety Monitoring Board (DSMB) and reviewed on a regular basis. The DSMB may request additional information as needed. Based on safety data, the DSMB may recommend to the Study Chairman to stop or otherwise modify the study. The Study Chairman will make the final decision after weighing the recommendation of the DSMB whether the study should then be stopped, modified or continued without change. The DSMB procedures will be described in the DSMB Charter.

VI. Risk/Benefit Analysis

Include research related risks and potential benefits (if any).

There is equipoise for the antithrombotic treatment intensity in patients with severe COVID-19. The table below summarizes the potential benefits and risks of intermediate-dose vs. prophylactic dose anticoagulation.

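### Line and CVVH filter thrombosis have two conflicting definitions; the primary-endpoint wording depends on the assigned dose, and the plan does not say which governs

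*Combined protocol and SAP*

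**What the plan says.** The sections Study Aims and Objectives and Primary Endpoint list the same thrombotic components. Two of them turn on a change of treatment: "Actionable line thrombosis requiring escalation of anticoagulation or removal or replacement of the line" and "CVVH Filter thrombosis requiring escalation of anticoagulation". For the line, removal or replacement is an alternative trigger. For the filter there is no alternative. Neither section says what dose escalation is measured from.

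The reportable-endpoints table in section III (Endpoint Definition) defines both differently. Line: "Arterial or central venous catheter thrombosis that results in removal or replacement of catheter or initiation of therapeutic anticoagulation". Filter: "Filter thrombosis requiring exchange in order to resume continuous veno-venous hemofiltration (CVVH) or resulting in cessation of CVVH".

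Section IV (Event Adjudication) says that suspected events "will be adjudicated based on pre-defined clinical definitions of venous thromboembolism, myocardial infarction, ischemic stroke, acute limb ischemia, clinically-actionable line thrombosis, and major bleeding". It does not say where those definitions are found, and the list omits filter thrombosis. It also says "All suspected events will be independently reviewed by two physicians blinded to randomized group assignment".

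On treatment after a clot, Study intervention gives "developing an event requiring therapeutic anticoagulation" as one reason to leave randomised therapy. Study assessment and activities says more broadly "Patients who develop a thrombotic event may have intensification of anticoagulation per clinical standard of care", with no level stated.

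**The concern.** The randomised factor is anticoagulation intensity, so an event defined by an increase in intensity has a different starting point in each arm. Take two patients with the same catheter clot, the line left in place, both treated at intermediate dose afterwards. The control patient has been escalated and meets the Primary Endpoint wording. The intermediate-arm patient has had no change and does not.

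For the filter, no other trigger offsets this. On CRRT the control regimen is a flat heparin rate, so any increase is an escalation. The intermediate infusion is run to an anti-Xa goal, so an increase could be read either as routine titration or as escalation.

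Selection turns on a lead of only 4 successes, so a small difference in scoring between arms could influence which regimen is selected, in favour of intermediate dosing.

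**Working it through.** **1. The two wordings side by side**

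| Component | Aims and Primary Endpoint | Section III | Depends on assigned dose? |
|---|---|---|---|
| Line thrombosis | Escalation, or line removed or replaced | Catheter removed or replaced, or therapeutic anticoagulation started | First: yes, through escalation. Second: no |
| CVVH filter thrombosis | Escalation only | Filter exchanged to resume CVVH, or CVVH stopped | First: yes. Second: no |

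**2. Reproducing the plan's own figures**

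Inputs, from Stopping and Decision rule and Table 1: 30 patients per arm before the first look, stop at a lead of at least 4, truncation at 50 pairs. Ties at truncation are split equally (my assumption; the plan resolves them on other grounds). Patients are treated as independent.

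Let D be the intermediate tally minus the control tally. At the first look D = X_I − X_C, with X_I ~ Bin(30, p_I) and X_C ~ Bin(30, p_C). Each later pair moves D by +1 with probability p_I(1 − p_C), by −1 with probability p_C(1 − p_I), and otherwise by 0. The calculation is exact, not simulated.

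| Scenario | Correct selection: exact (Table 1) | Expected N: exact (Table 1) | Truncation: exact (Table 1) |
|---|---|---|---|
| 0.35 v 0.20 | 95.2% (95.1%) | 68.4 (68.4) | 10.4% (10.2%) |
| 0.30 v 0.20 | 87.3% (87.1%) | 73.9 (74.0) | 21.3% (21.5%) |
| 0.20 v 0.20 | 50.0% (50.2%) | 83.0 (83.0) | 43.4% (43.5%) |

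Table 1 is reproduced, so the same calculation can be used for the illustration.

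**3. Effect of one-sided rescoring**

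Let d be the share of control patients who would otherwise be successes but are scored as failures only because of a step up to intermediate dosing. Then p_C becomes p_C(1 − d) and p_I is unchanged. The documents give no value for d; the range below is assumed. Example: d = 10% at a true rate of 0.20 gives 0.20 × 0.90 = 0.18, which is 30 × 0.02 = 0.6 patients per 30.

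| d (assumed) | Intermediate selected, both true rates 0.20 | Intermediate selected, both 0.35 | Correct selection, control truly better (0.35 v 0.20) |
|---|---|---|---|
| 0 | 50% | 50% | 95.2% |
| 1% | 51% | 51% | 94.8% |
| 5% | 55% | 57% | 93.1% |
| 10% | 60% | 64% | 90.3% |
| 20% | 70% | 77% | 82.2% |

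**4. If the rescoring is not one-sided**

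If the same share d of successes is lost in both arms, correct selection at 0.35 v 0.20 is 94.0% at d = 10% and 92.5% at d = 20%. The harm comes from the difference between arms, not from the component itself.

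**The case against.** A reader might infer that the event threshold is in fact lower in the control arm, that the tallies are therefore biased, and that the design's 90% guarantee is lost. The documents do not support that, for these reasons.

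- Section III is the section devoted to endpoint definitions and the only place with detailed ones. It is natural, though nowhere stated, to read section IV as referring to it. On that reading the asymmetry vanishes for both components.
- A step from prophylactic to intermediate dosing is not among the listed reasons for leaving randomised therapy. The general statement on intensification may allow it, but nothing shows that it is expected or common.
- Line removal or replacement counts in both arms, and so does escalation beyond intermediate dosing. Section III also counts upper- and lower-extremity vein thrombosis on duplex as deep venous thrombosis, so some catheter clots could be events in either arm anyway.
- Escalation is undefined, so a rate increase in the intermediate arm might be scored too. If clinicians step up one level in either arm, both patients are events.
- The share d is wholly assumed. An affected patient must be alive, free of every other event and, for a line clot, have kept the line. Of the values shown, only 20% takes correct selection below 90%.

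All of this stands as a limit on size and certainty. It does not remove the conflict, because no text chooses between the wordings and the dose-dependent one stands under the Primary Endpoint heading.

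Two further defences are weaker. Blinded review does not help: escalation cannot be judged without knowing the starting dose, which points to the arm, and an asymmetric definition applied correctly is still asymmetric. The planned sensitivity analyses excluding CRRT patients and anticoagulation deviations belong to the models for the first 60 patients, not to the selection rule. Excluding deviations would also remove the affected control failures selectively.

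**Conclusion.** The plan gives two incompatible definitions for two components of its primary endpoint and does not say which governs. One of them can score the same clot differently by arm. That much follows from the text.

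Bias towards the intermediate arm is conditional. It needs the Primary Endpoint wording to govern, control patients to be stepped up only as far as intermediate dosing, and comparable intermediate-arm patients to go unscored. Its size cannot be derived from the documents. Under one-sided rescoring of 1% to 20% of control successes, selection of intermediate with no true difference at 0.20 runs from 51% to 70%, and correct selection with control truly better runs from 94.8% down to 82.2%. These figures show sensitivity to d and do not estimate it. The correction is still worthwhile: any such bias would favour the experimental arm, it would act on the tally that decides the trial, and neutral wording is already in the document.

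**What to change.** 1. In Study Aims and Objectives, Primary Endpoint and section III, state that the existing section III definitions govern line thrombosis and CVVH filter thrombosis in the primary endpoint. Delete the escalation trigger from the first two sections.
2. For the filter, use section III's exchange-or-cessation wording. Carrying the line's therapeutic-anticoagulation trigger over to the filter would create a third definition and could drop clots that force a filter exchange.
3. Add CVVH filter thrombosis to the adjudicated definitions listed in section IV.
4. Instruct the clinical events committee that a dose change between or within the study regimens is not by itself an event, and record such changes on the CRF.
5. Rescore existing line and filter events under the governing definition, blinded to arm.

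Cost: wording in three sections and the adjudication instructions, plus rescoring of events already collected, since recruitment has begun. The number of events in the composite may change slightly. This concerns scoring only and alters no patient's treatment.

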Randomization procedures	Patients, when eligible, will be enrolled to the study at the “first-come-first-serve” basis. All the participating ICUs can have 2 possible “room type”: negative pressure rooms and non-negative pressure rooms. Each of the participating ICUs will be divided into either two or four clusters as follows. Any ICU with only one room type (i.e., it only has negative pressure rooms or only has non-negative pressure rooms) will be divided into 2 clusters. For ICUs that contain both room types (i.e., it has negative pressure rooms and non-negative pressure rooms), we will divide that ICU into 4 clusters with two clusters for each room type. Two clusters within each ICU and each room type will then be randomized to either of the study arms. Enrolled patients will receive the treatment according to the cluster of ICU they are assigned. Post-randomization pairing scheme will be employed to form the pairs if the stopping criterion is not reached at the time that first 60 outcomes have been observed. As the hospital administration changed the room type to accommodate the decrease of COVID patients (e.g., some negative

	
pressure rooms were changed to non-negative pressure rooms), we currently recruitment included more patients in the prophylactic dose group than those of the intermediate dose group. At the recommendation of the DSMB, in each ICU and each room type, we will randomize “intermediate dose rooms” and “prophylactic dose rooms” in a 3:1 ratio until we reach enrollment of 30 patients for one group and we will then only assign patients to the other group until we achieve the recruitment of 30 patients that group as well. After we recruit 30 patients for each arm, the ratio of the rooms will be changed back to 1:1 (intermediate vs. prophylactic) for the subsequent recruitment.

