the treatment according to the cluster of ICU they are assigned. Post-randomization pairing scheme will be employed to form the pairs if the stopping criterion is not reached at the time that first 60 outcomes have been observed. As the hospital administration changed the room type to accommodate the decrease of COVID patients (e.g., some negative pressure rooms were changed to non-negative pressure rooms), we currently recruitment included more patients in the prophylactic dose group than those of the intermediate dose group. Pending the approval of DSMB, in each ICU and each room type, we will randomize “intermediate dose rooms” and “prophylactic dose rooms” in a 3:1 ratio until we reach enrollment of 30 patients for one group and we will then only assign patients to the other group until we achieve the recruitment of 30 patients that group as well. After we recruit 30 patients for each arm, the ratio of the rooms will be changed back to 1:1 (intermediate vs. prophylactic) for the subsequent recruitment.

Success tallies:

Each time the follow-up for each patient in a pair is complete and a “good” or “poor” outcome is determined for each based on the composite primary outcome, the pair becomes “observed” and is available for sequential monitoring by adding to a running tally of the “good” outcomes for each intervention. These *success tallies* are used for the stopping rule.

Stopping and Decision rule: The criterion for stopping is a *difference of 4 or more between the tallies* if this occurs at or before 60 patients’ outcomes have been observed. At that time, intervention with the largest success tally is selected as the preferred intervention. However, we will not stop the procedure and make a decision before the outcomes of the first 60 patients have become available. In addition, if the criterion for stopping has not been reached at or before 100 outcomes have been observed, the trial will stop by *truncation* with a maximum of 100 patients. At that time, intervention with the largest success tally is selected as the preferred intervention. If there are ties for the largest success tally at time of truncation, we will select the intervention according to other considerations (safety, better secondary outcomes, etc.).

Incomplete pairs:

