To avoid bias in statistical inference due to bias in sampling, *only* the first 60 patients will be included in this set of analysis. Details explain why bias occurs and how it will affect the statistical inference can also be found in the supplemental appendix. We will use the data from these 60 patients to generate the proportions of patients with the events specified as primary and secondary outcomes. We will also report the descriptive statistics (mean, median, interquartile range) for the time to ICU discharge. Graphical display of the data will be done as well. To compare the intervention effect between the two study groups on the primary and secondary outcomes, we will use generalized linear model with identity link function for continuous variables and logit link function for dichotomous variables following the intent-to-treat principle. Covariates in these models include intervention group indicator, ICU indicators, and the potential confounding factors. The pre-specified potential confounders are age, sex, weight, estimated glomerular filtration rate (eGFR), concomitant treatment with an IL-6 inhibitor, and concomitant treatment with corticosteroids. Generalized estimating equations methodology will be employed to account for the within-ICU correlation for subject assignment to the same ICU area. The key parameter of interest is the regression coefficient corresponding to the intervention group indicator which is the mean difference for continuous outcomes and log-odds ratio for dichotomous outcomes and it represents intervention effect of intermediate-dose anticoagulation compared with that of prophylactic anticoagulation. To report the trial findings, we will present the mean difference and odds ratio when appropriate and their corresponding p-values and 95% confidence intervals. Several pre-specified sensitivity analyses will be conducted: (1) excluding the patients who undergo CRRT during the study period; (2) excluding patients who experienced deviation in anticoagulation from randomized treatment arm; (3) analyzing the patients as the treatment they actually received. Additional sensitivity analysis will also be conducted to include covariates found imbalanced between the two intervention groups.

Operating characteristics of the Study Design

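### Within the first 60 patients arm is tied to enrolment period, so the plan's claim of an unbiased first-60 analysis covers optional stopping but not a time trend

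*Combined protocol and SAP*

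**What the plan says.** Section II, Randomization procedures, and the matching Sampling rule in section VIII describe three allocation phases before each arm has 30 patients.

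- **Phase 1, even allocation by cluster.** "Two clusters within each ICU and each room type will then be randomized to either of the study arms". The hospital then "changed the room type to accommodate the decrease of COVID patients", and the text reports that "we currently recruitment included more patients in the prophylactic dose group than those of the intermediate dose group". No counts are given.
- **Phase 2.** Intermediate and prophylactic rooms are randomised "in a 3:1 ratio until we reach enrollment of 30 patients for one group and we will then only assign patients to the other" group.
- **Phase 3.** Only that other arm recruits until it also has 30. The 1:1 ratio returns only after that.

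The two places differ on status (DSMB recommendation in one, DSMB approval pending in the other) but not on the allocation.

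The first-60 model appears in the Design row of the outline and in section VIII. "Covariates in these models include intervention group indicator, ICU indicators, and the potential confounding factors". The confounders are age, sex, weight, eGFR, IL-6 inhibitor and corticosteroids, with GEE for within-ICU correlation. On sensitivity: "Several pre-specified sensitivity analyses will be conducted: (1) excluding the patients who undergo CRRT during the study period", followed by excluding treatment deviations and by an as-treated analysis. Last: "Additional sensitivity analysis will also be conducted to include covariates found imbalanced between the two intervention groups". Neither enrolment period nor room type is named.

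General Design holds back selection until 60 patients so that unbiased estimates will exist for each arm. Minimizing Selection Bias concludes that estimating and testing on these 60 is unbiased because they are recruited with no comparison of outcomes. Selection itself uses raw tallies: a completed pair "is available for sequential monitoring by adding to a running tally of the" good outcomes in each arm.

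**The concern.** Prophylactic patients are over-represented before the change and intermediate patients during the 3:1 phase. The last patients all belong to one arm and have no concurrent comparator. If the success rate moved during enrolment for reasons unrelated to dose, part of that movement would appear as a dose effect.

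The plan's argument likens the first 60 to a fixed-sample design. Not looking at outcomes does make the sample size independent of them. It does not make arm independent of calendar time once the ratio changes partway.

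At stake are the first-60 estimate, confidence interval and p-value, which the plan presents as its unbiased results. The tally at 60 is exposed too: with 30 per arm, the unadjusted difference equals the tally lead divided by 30. The plan reports a falling case load and room reclassification in this window, so conditions were not constant, but it reports no trend in outcome.

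**Working it through.** **1. The plan's own figure.** Table 1, Scenario 1 (0.35 against 0.20, lead of 4, minimum 60, maximum 100) gives expected N 68.4, correct selection 95.1%, truncation 10.2% and a decision at 60 in 62.6%. An exact calculation (difference of two Binomial(30) tallies, then a pairwise walk to 50 pairs, ties split) gives 68.41, 95.2%, 10.4% and 62.6%. The table reproduces. It assumes a constant success rate in each arm, so it does not address drift.

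**2. Inputs that must be assumed.** The documents give no split at the change and no trend. Assumed here: identical arms; success moving from 0.20 to 0.35 (the plan's two design rates); 75% of phase 2 patients to intermediate; phase 1 patients in random order; and the prophylactic/intermediate splits below. Bias is intermediate minus prophylactic in the unadjusted success difference.

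*Step at the change.* With P and I enrolled before it, the post-change shares are (30 - I)/30 and (30 - P)/30, so bias = 0.15 × (P - I)/30.

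*Linear drift over 60 enrolments.* Bias = (0.15/59) × D, where D is the simulated difference in mean enrolment position.

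| Split P/I | D | Linear bias | Step bias |
|---|---|---|---|
| 12/6 | -1.7 | -0.004 | 0.15 × 6/30 = +0.030 |
| 18/12 | +2.6 | +0.007 | 0.15 × 6/30 = +0.030 |
| 20/12 | +5.8 | +0.015 | 0.15 × 8/30 = +0.040 |
| 24/10 | +14.1 | +0.036 | 0.15 × 14/30 = +0.070 |
| 28/10 | +18.7 | +0.048 | 0.15 × 18/30 = +0.090 |

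Simulation error puts the 12/6 linear value between -0.003 and -0.005. Falling rates reverse every sign.

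**3. Test.** For the four larger splits, with rates ending at 0.30 or 0.35, a nominal 5% unadjusted test rejects in 4.9% to 6.9% of trials under linear drift and 5.3% to 12.2% under the step.

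**4. Planned covariates.** A logistic model of the planned type was simulated with four assumed ICUs, no within-ICU correlation and true OR 1. If no listed covariate carries the trend, the mean OR is 1.03 to 1.30 (linear) or 1.17 to 1.62 (step). If corticosteroid use rising from 20% to 80% carries half of it, the OR is 1.01 to 1.12 or 1.06 to 1.23. If it carries all, 0.99 to 1.02.

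**5. Selection.** If prophylactic is truly better by OR 2.15, correct selection stays at 92% to 96% under linear drift. It falls below 90% only for a step at 24/10 (88.5%) or 28/10 (84.5%, or 89.3% if the step ends at 0.30).

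**6. What period adjustment buys.** At a flat rate of 0.275 the unadjusted SE is √(2 × 0.275 × 0.725/30) = 0.115. Stratifying by period uses the sum of nI·nP/(nI + nP), and the single-arm phase adds nothing. For 20/12 with mean phase 2 counts 17.5 and 5.8: 12 × 20/32 + 17.5 × 5.8/23.3 = 7.50 + 4.36 = 11.86, against 15 for 30:30. That gives SE √(0.199/11.86) = 0.130. Across the four larger splits the simulated SE is 0.13 to 0.15. With additive room type and 3 or 5 assumed ICUs as well it is 0.135 to 0.160.

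Stratification removes almost all the bias when phase 1 patients arrive in random order. If the prophylactic excess instead builds up late in phase 1, linear drift leaves the stratified estimate biased by about -0.004 to -0.028. At 18/12 and 20/12 that is more than the unadjusted bias.

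**The case against.** The strongest case against acting is that drift is hypothetical and the simpler estimate usually does better. The unadjusted difference has lower RMSE than the period-stratified one in 14 of 16 drift settings (four larger splits, linear or step, ending at 0.30 or 0.35); at 28/10 with linear drift to 0.35 it is 0.125 against 0.149. The test is barely disturbed by linear drift, and selection, the trial's primary goal, holds up. Corticosteroid and IL-6 inhibitor terms may already carry a treatment-era trend. The imbalanced-covariates analysis could admit period, which the allocation would tend to unbalance.

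Most of this stands, and it limits the remedy to a companion estimate. It does not rescue the claim of unbiasedness, which the allocation does not guarantee. Leaving period to an unnamed analysis chosen after imbalance is seen is not pre-specification.

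Three stronger readings are tempting, and none is supported:

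- *The first-60 estimate is biased, and towards intermediate.* The documents report no outcome trend and no split, and at 12/6 a linear rise gives a small bias the other way.
- *Adding period would remove the bias.* It does not if the allocation mix shifted within phase 1, which room reclassification makes plausible.
- *Agreement with and without period would show robustness.* At true OR 2.15, a check on matching sign and on the adjusted value lying inside the other version's 95% CI flags 8% to 16% of trials without drift and about the same under linear drift.

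**Conclusion.** The point holds as a gap between claim and design. Within the first 60, arm is associated with enrolment period. The stated grounds for unbiasedness cover optional stopping only, and no analysis names period or room type.

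With identical arms and success moving from 0.20 to 0.35, the unadjusted bias is about -0.005 to +0.05 for linear drift and +0.03 to +0.09 for a step, which is an extreme shape. These figures rest on assumed splits and an assumed trend, and they are not bounds. The planned covariates may absorb some, all or none of the effect.

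A reader might infer that the selection rule is undermined. Under linear drift it is not: correct selection stays above the plan's 90% target, and only an extreme step at a very uneven split takes it below. The change is worth making because it is cheap and concerns the results that the plan labels unbiased.

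**What to change.** 1. In Minimizing Selection Bias and General Design, limit the unbiasedness statements to bias from optional stopping, or make them conditional on no time trend.
2. Keep the planned first-60 model, the allocation and the stopping rule. Before outcomes by arm are compared, pre-specify one companion first-60 success difference with additive terms for allocation period (1:1, 3:1, single-arm), room type at enrolment and ICU. Show it beside the same estimate without period and room type. Keep the terms additive and few: 60 patients at 0.20 to 0.35 give only 60 × 0.20 = 12 to 60 × 0.35 = 21 successes. Present it as descriptive, with no agreement rule and no label of robustness. State that it does not remove drift within a period and that it often has higher RMSE than the unadjusted estimate.
3. Report counts and successes by arm and period beside the tally at 60 and at selection.

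The cost is a little analysis work on enrolment date, room type and arm, which are already needed to run the allocation. The companion estimate has a wider SE, about 0.13 to 0.16 against 0.115 unadjusted, which is why it accompanies the planned model and does not replace it.
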